13.4. Reporting Adverse Events

The Investigator will notify the Sponsor of an adverse event by e-mail, facsimile, or telephone as soon as possible and no later than 24 hours from discovery for any serious /significant adverse events, and 2 days from discovery for any non-significant adverse event. In addition, a written report will be submitted by the Principal Investigator to the IEC/IRB according to their requirements (Section 13.4.2). The report will comment whether the adverse event was considered to be related to the test article, study treatment or study procedures.

13.4.1. Reporting Adverse Events to Sponsor

Serious/Significant Adverse Events

The Investigator will inform the sponsor of all serious/significant adverse events occurring during the study period as soon as possible by e-mail, fax, or telephone, but no later than 24

Clinical Study Protocol

Johnson & Johnson Vision Care, Inc.

hours following discovery of the event. The Investigator is obligated to pursue and obtain information requested by the Sponsor in addition to that information reported on the eCRF. All subjects experiencing a serious/significant adverse event must be followed up and all outcomes must be reported.

When medically necessary, the Investigator may break the randomization code to determine the identity of the treatment that the subject received. The Sponsor and study monitor should be notified prior to unmasking the test articles.

In the event of a serious/significant adverse event, the Investigator must:

- Notify the Sponsor immediately.
- Obtain and maintain in the subject's records all pertinent medical information and medical judgment for colleagues who assisted in the treatment and follow-up of the subject.
- Provide the Sponsor with a complete case history which includes a statement as to whether the event was or was not related to the use of the test article.
- Notify the IEC/IRB as required by the IEC/IRB reporting procedure according to national regulations.

Unanticipated (Serious) Adverse Device Effect (UADE)

In the event of an Unanticipated (Serious) Adverse Device Effect (UADE), the Investigator will submit a report of the UADE to the Sponsor and IEC/IRB as soon as possible, but no later than 24 hours after the Investigator first learns of the effect. This report is in addition to the immediate notification mentioned above.

The Sponsor must conduct an evaluation of the UADE and must report the results of the evaluation to FDA, the IEC/IRB and participating Investigators within 10 working days after the Sponsor first receives notification of the effect.

Non-Serious Adverse Events

All non-serious adverse events, including non-serious adverse device effects, will be reported to the sponsor by the Investigator no later than 2 days from discovery.

13.4.2. Reporting Adverse Events to the Responsible IEC/IRB and Health Authorities

Adverse events that meet the IEC/IRB requirements for reporting must be reported within the IEC/IRB's written guidelines. Each clinical site will refer to and follow any guidelines set forth by their Approving IEC/IRB. Each clinical site will refer to and follow any guidelines set forth by their local governing Health Authorities.

The Sponsor will report applicable Adverse Events to the local health authorities according the written guidelines, including reporting timelines.

13.4.3. Event of Special Interest

None

Clinical Study Protocol

Johnson & Johnson Vision Care, Inc.

13.5. Reporting of Pregnancy

Subjects reporting pregnancy (by self-report) during the study will be discontinued after the event is recorded as an Adverse Event. Once discontinued, pregnant participants and their fetuses will not be monitored for study related purposes. At the Investigator's discretion, the study participant may be followed by the Investigator through delivery. However, this data will not be collected as part of the clinical study database. Pregnant participants are not discontinued from contact lens or solution related studies for safety concerns, but due to general concerns relating to pregnancy and contact lens use. Specifically, pregnant women are discontinued due to fluctuations in refractive error and/or visual acuity that occur secondary to systemic hormonal changes, and not due to unforeseen health risks to the mother or fetus.

14. STATISTICAL METHODS

14.1. General Considerations

Statistical Analysis will be undertaken by the sponsor or under the authority of the sponsor. A general description of the statistical methods to be implemented in this clinical trial is outlined below.

All data summaries and statistical analyses will be performed using the SAS software Version 9.4 or higher (SAS Institute, Cary, NC). Throughout the analysis of data, the results for each subject/eye will be used when available for summarization and statistical analysis. Unscheduled visits will be summarized separately and will be excluded from the statistical analysis.

Summary tables (descriptive statistics and/or frequency tables) will be provided for all baseline variables, efficacy variables and safety variables as appropriate. Continuous variables will be summarized with descriptive statistics (n, mean, standard deviation [SD], median, minimum and maximum). Frequency count and percentage of subjects or eyes within each category will be provided for categorical data.

Summaries will be presented by study lens type and will be performed separately by completion status (Safety Population, Per-Protocol Population or Intent-to-Treat Population).

14.2. Sample Size Justification

This study was not designed or powered to test non-inferiority of the Test lens relative to the Control lens. Instead the sample size was chosen by the study responsible clinician. Historical data for the Control lens from [REDACTED] at the 1-week follow-up was utilized in the power calculation. The mean and standard deviation for the Control was 60.1 and 19.58, respectively. Assuming that the Test and Control will have similar performance with respect to CLUE vision scores, the table below provide the power for different scenarios of effect size and intra-class correlation.

Table 5: Statistical Power Analysis to test for Non-inferiority of the Test relative to the Control

Clinical Study Protocol
Johnson & Johnson Vision Care, Inc.

Effect Size	Intra-class correlation	Power
0	0.3	0.675
0	0.6	0.871
0	0.8	0.989
1	0.3	0.809
1	0.6	0.954
1	0.8	0.999
2	0.3	0.902
2	0.6	0.987
2	0.8	>.999
3	0.3	0.957
3	0.6	0.997
3	0.8	>.999

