14.3. Analysis Populations

Safety Population:

All subjects who were administered any test article excluding subjects who drop out prior to administering any test article. At least one observation should be recorded.

Per-Protocol Population:

All subjects who have successfully completed all visits and did not substantially deviate from the protocol as determined by the trial cohort review committee prior to database hard lock (Per-Protocol Population). Justification of excluding subjects with protocol deviations in the Per-Protocol Population set will be documented in a memo to file.

Intent-to-Treat (ITT) Population:

All subjects regardless of actual treatment and subsequent withdrawal from study or deviation from protocol. At least one observation should be recorded.

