14.5. Primary Analysis

All primary analysis will be conducted on the Per-protocol population.

CLUE Vision

CLUE vision scores at the 2-week follow-up will be analyzed using a linear mixed model adjusting for baseline values as a covariate. Sequence of lens wear, study period, lens type will be included as fixed effects. Other factors such as, race, gender or ADD power may be included in the model as covariates when appropriate. Site will be included as a random effect (G-side). The covariance between residual errors from the same subject across study periods will be modeled using either homogenous compound symmetry (CS) or unstructured (UN). The

Clinical Study Protocol

Johnson & Johnson Vision Care, Inc.

structure that returns the lowest finite-sample corrected Akaike's Information criterion⁷ will be selected as the structure that best fits the model. The Kenward and Roger method, (Kenward and Roger, 1997)⁸ will be used for the denominator degrees of freedom.

Comparisons between the Test and Control lens at the 2-week follow-up evaluation will be carried out using two-sided 95% confidence intervals constructed for the least-square mean difference (Test minus Control).

Primary hypothesis 1:

The null and alternative hypothesis for CLUE vision to test for superiority of the Test lens relative to the pre-defined threshold of 40 is as follows:

$$H_0: \mu_{Test} \leq 40$$
$$H_A: \mu_{Test} > 40$$

Superiority will be declared if the lower limit of the 95% confidence interval of the adjusted mean for the Test lens is greater than 40. i.e. $P(\mu_{Test} > 40) \geq 0.975$.

Primary Hypothesis 2:

The null and alternative hypothesis for CLUE vision to test for non-inferiority of the Test lens relative the Control lens is as follows:

$$H_0: \mu_{Test} - \mu_{Control} \leq -5$$
$$H_A: \mu_{Test} - \mu_{Control} > -5$$

Non-inferiority will be declared if the lower limit of the 95% confidence interval for the least-square mean difference is greater than -5. i.e. $P(\mu_{Test} - \mu_{Control} > -5) \geq 0.975$.

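### Table 5's non-inferiority power does not follow from the plan's own SD, margin, sample size and decision rule, and is overstated (0.871 printed, 0.65 recomputed, at effect 0 and ICC 0.6)

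*Combined protocol and SAP*

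**What the plan says.** Section 14.2 starts with a disclaimer: "This study was not designed or powered to test non-inferiority of the Test lens relative to the Control lens". It adds that the responsible clinician chose the sample size. It then gives the basis of a power calculation, "The mean and standard deviation for the Control was 60.1 and 19.58, respectively", and introduces the scenarios with "Assuming that the Test and Control will have similar performance with respect to CLUE vision scores". The result is "Table 5: Statistical Power Analysis to test for Non-inferiority of the Test relative to the Control", which covers effects of 0 to 3 and ICCs of 0.3, 0.6 and 0.8. Neither n nor alpha is stated for the table.

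The other inputs are elsewhere in the protocol:

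- **Margin:** 5 CLUE points (Section 2.3, Primary Hypothesis 2).
- **Design and size:** a 2×2 crossover with about 85 enrolled and 70 expected to complete (Sections 4.1 and 4.3).
- **Analysis set:** "All primary analysis will be conducted on the Per-protocol population" (Section 14.5). Section 14.3 defines that population as "All subjects who have successfully completed all visits and did not substantially deviate from the protocol".
- **Decision rule:** "Comparisons between the Test and Control lens at the 2-week follow-up evaluation will be carried out using two-sided 95% confidence intervals", and "Non-inferiority will be declared if the lower limit of the 95% confidence interval for the least-square mean difference is greater than -5" (Section 14.5). The same section restates the criterion as a probability of at least 0.975.

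Section 2.3 makes the study objective depend on meeting every primary and secondary hypothesis.

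**The concern.** A power table should follow from the plan's SD, margin, size and test. This one appears too favourable for 70 completers judged on a two-sided 95% interval.

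Table 5 is the only figure in the protocol for the chance of meeting Primary Hypothesis 2, and the study cannot succeed without that hypothesis. Similar performance of the two lenses is most naturally the effect-0 rows. A reader who takes ICC 0.6 there would put the chance at 87%.

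**Working it through.** **Inputs.** SD 19.58 (14.2); margin 5 (2.3, 14.5); n = 70 completers (4.3), because the primary analysis is per-protocol; one-sided alpha 0.025 (14.5). Effect is read as Test minus Control in CLUE points, positive favouring Test, which fits the rising printed power. ICC is read as the correlation between a subject's two periods.

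**Formula.** For a paired comparison, SE = 19.58 × √(2(1 − ICC)/n). The noncentrality is (5 + effect)/SE. Power comes from the noncentral t distribution with n − 2 degrees of freedom.

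**One cell in full: effect 0, ICC 0.6, n = 70.**

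- SE = 19.58 × √(0.8/70) = 2.093
- Noncentrality = 5/2.093 = 2.389
- Critical t (68 df, one-sided 0.025) = 1.995
- Power = 0.654. The normal approximation, Φ(2.389 − 1.960), gives 0.666, so the choice of t or z does not explain the gap.
- Table 5 prints 0.871.

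**Whole table, printed / recomputed (n = 70, one-sided 2.5%).**

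| Effect | ICC 0.3 | ICC 0.6 | ICC 0.8 |
|---|---|---|---|
| 0 | 0.675 / 0.429 | 0.871 / 0.654 | 0.989 / 0.915 |
| 1 | 0.809 / 0.570 | 0.954 / 0.807 | 0.999 / 0.979 |
| 2 | 0.902 / 0.703 | 0.987 / 0.909 | >.999 / 0.997 |
| 3 | 0.957 / 0.813 | 0.997 / 0.965 | >.999 / >.999 |

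Eleven of twelve cells are too high, nine of them by 3 percentage points or more. Only effect 3 with ICC 0.8 agrees. At each ICC the gap is largest at effect 0: 25, 22 and 7 points.

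**Can the plan's own sizes reproduce the table?** Effect 0, SD 19.58:

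| n, one-sided alpha | ICC 0.3 | ICC 0.6 | ICC 0.8 |
|---|---|---|---|
| Printed | 0.675 | 0.871 | 0.989 |
| 70, 0.025 | 0.429 | 0.654 | 0.915 |
| 70, 0.05 | 0.557 | 0.764 | 0.955 |
| 85, 0.025 | 0.503 | 0.740 | 0.957 |
| 85, 0.05 | 0.629 | 0.833 | 0.980 |

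None does. The most generous row assumes no dropout and a looser rule than Section 14.5, and it still falls short.

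**What does reproduce it?** I solved back from the ten cells printed as exact values. Three fits, all at one-sided 5%, match every cell to within about 0.0006:

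- n = 96 with SD 19.58
- n = 70 with SD 16.68
- n = 85 with SD 18.41

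The table therefore identifies alpha but cannot separate n from SD. With alpha forced to 0.025, the best single SD at n = 70 (14.75) leaves errors up to 0.018, too large for values printed to three decimals.

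**How much is due to alpha?** At n = 70 and effect 0, moving from one-sided 2.5% to 5% adds 12.8, 11.1 and 4.1 points at ICC 0.3, 0.6 and 0.8, about half of each gap. The rest depends on the unstated n or SD.

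**ICC needed for 80% power with equal lenses.** About 0.72 under the plan's size and rule. The inputs that reproduce the printed table imply about 0.50.

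**The case against.** The strongest reply is that Section 14.2 disclaims the table: the study was not powered for non-inferiority and a clinician set the size, so no decision rested on these figures. That limits the consequence and stands to that extent. It does not make the figures correct, and Section 2.3 still makes non-inferiority a condition of success.

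Second, the table states no n, so the size of the overstatement depends on taking 70 subjects and SD 19.58. This also stands: an SD of about 16.7 with 70 subjects would fit the printed cells. But that SD appears nowhere in the documents, and the fit still needs one-sided 5%. Applying the Section 14.5 rule even to 96 subjects with SD 19.58 gives 0.791 at effect 0 and ICC 0.6, not 0.871.

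Third, Section 14.4 sets an overall type I error rate of 5%, which may be where the alpha came from. That could explain a slip in sidedness, but it does not override the explicit 0.975 criterion, and it leaves the n or SD part of the gap unexplained.

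Fourth, the planned model adjusts for baseline, which might reduce variance. The one pre-study CLUE score per subject is the same in both periods, so it should do little to the within-subject comparison, and Section 14.2 mentions no such reduction.

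Finally, the expected ICC is not stated. At ICC 0.8 the gap at effect 0 is 7 points and power is still 0.91, so the 22-point figure is one scenario among several. Reading similar performance as effect 0 is also an interpretation, since the same sentence introduces all four effects.

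**Conclusion.** The concern holds: Table 5 is wrong as written. It reflects a one-sided 5% test while Section 14.5 applies one-sided 2.5%, and that conflict does not depend on which n or SD was used. With SD 19.58 it also matches neither 70 nor 85 subjects; about 96 would be needed, more than will be enrolled. That n is inferred from the fit and is not stated in the plan.

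The size of the overstatement is conditional on SD 19.58, 70 analysed completers, the paired t calculation and no variance reduction from covariates. On those terms it runs from 25 points (effect 0, ICC 0.3) to almost nothing in the highest-power cells. Type I error, enrolment and the treatment estimates are untouched. This should be fixed, but it does not threaten the validity of the trial.

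**What to change.** Recompute Table 5 for 70 completers at one-sided 2.5% (the lower limit of the two-sided 95% interval), and print n, alpha and SD with it. If another SD or n was intended, state it and its source; the table must still be recomputed at one-sided 2.5%. Add a sentence to Section 14.2 saying that this is the power for Primary Hypothesis 2, which Section 2.3 requires to be met.

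The cost is one replaced table and one added sentence. The stated power becomes less favourable. Enrolment, the decision rule and the status of the hypothesis need no change.

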14.3. Analysis Populations

Safety Population:

All subjects who were administered any test article excluding subjects who drop out prior to administering any test article. At least one observation should be recorded.

Per-Protocol Population:

All subjects who have successfully completed all visits and did not substantially deviate from the protocol as determined by the trial cohort review committee prior to database hard lock (Per-Protocol Population). Justification of excluding subjects with protocol deviations in the Per-Protocol Population set will be documented in a memo to file.

Intent-to-Treat (ITT) Population:

All subjects regardless of actual treatment and subsequent withdrawal from study or deviation from protocol. At least one observation should be recorded.

14.4. Level of Statistical Significance

All planned analysis for this study will be conducted with an overall type I error rate of 5%.

14.5. Primary Analysis

All primary analysis will be conducted on the Per-protocol population.

CLUE Vision

CLUE vision scores at the 2-week follow-up will be analyzed using a linear mixed model adjusting for baseline values as a covariate. Sequence of lens wear, study period, lens type will be included as fixed effects. Other factors such as, race, gender or ADD power may be included in the model as covariates when appropriate. Site will be included as a random effect (G-side). The covariance between residual errors from the same subject across study periods will be modeled using either homogenous compound symmetry (CS) or unstructured (UN). The

Clinical Study Protocol

Johnson & Johnson Vision Care, Inc.

structure that returns the lowest finite-sample corrected Akaike's Information criterion⁷ will be selected as the structure that best fits the model. The Kenward and Roger method, (Kenward and Roger, 1997)⁸ will be used for the denominator degrees of freedom.

Comparisons between the Test and Control lens at the 2-week follow-up evaluation will be carried out using two-sided 95% confidence intervals constructed for the least-square mean difference (Test minus Control).

Primary hypothesis 1:

The null and alternative hypothesis for CLUE vision to test for superiority of the Test lens relative to the pre-defined threshold of 40 is as follows:

$$H_0: \mu_{Test} \leq 40$$
$$H_A: \mu_{Test} > 40$$

Superiority will be declared if the lower limit of the 95% confidence interval of the adjusted mean for the Test lens is greater than 40. i.e. $P(\mu_{Test} > 40) \geq 0.975$.

Primary Hypothesis 2:

The null and alternative hypothesis for CLUE vision to test for non-inferiority of the Test lens relative the Control lens is as follows:

$$H_0: \mu_{Test} - \mu_{Control} \leq -5$$
$$H_A: \mu_{Test} - \mu_{Control} > -5$$

Non-inferiority will be declared if the lower limit of the 95% confidence interval for the least-square mean difference is greater than -5. i.e. $P(\mu_{Test} - \mu_{Control} > -5) \geq 0.975$.

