2.3. Hypotheses

All primary and secondary hypotheses must be met in order to satisfy the objective of this study.

Primary Hypotheses

1. After approximately 2 weeks of wear, the mean overall quality of vision score of the Test lens will be statistically better than 40 points on CLUE scale.
2. After approximately 2 weeks of wear, the Test lens will be non-inferior to the Control lens with respect to the overall quality of vision score. A non-inferiority margin of 5 points will be used.

Secondary Hypotheses

1. After approximately 2 weeks of wear, the mean distance visual acuity score of the Test lens will be statistically lower than 0.00 on logMAR scale.
2. After approximately 2 weeks of wear, the mean intermediate visual acuity score of the Test lens will be statistically lower than 0.17 on logMAR scale.
3. After approximately 2 weeks of wear, the mean near visual acuity score of the Test lens will be statistically lower than 0.17 on logMAR scale.

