4.3. Enrollment Target and Study Duration

A total of approximately 85 eligible subjects will be enrolled with 70 targeted to complete the study. The study will last approximately 2-4 months.

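### Primary hypothesis 1 concerns the mean Test CLUE score, but its baseline-adjusted interval leaves out sampling error in the mean baseline and is too narrow if baseline and Test scores are well correlated

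*Combined protocol and SAP*

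**What the plan says.** Section 2.3 states primary hypothesis 1 as: "the mean overall quality of vision score of the Test lens will be statistically better than 40 points on CLUE scale". Nothing there conditions on the baseline scores of the subjects who happen to enrol.

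Section 14.5 sets the model: "CLUE vision scores at the 2-week follow-up will be analyzed using a linear mixed model adjusting for baseline values as a covariate". Sequence, period and lens are fixed effects, site is random, and race, gender or ADD power may be added. Hypothesis 1 succeeds if the "lower limit of the 95% confidence interval of the adjusted mean for the Test lens is greater than 40", which the section equates with a probability of at least 0.975. The section does not say at which baseline value the adjusted mean is evaluated.

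Baseline CLUE is taken once, at Visit 1, on habitual lenses (Table 3 and step 1.9). The Visit 4 steps contain no CLUE. The primary analysis uses the per-protocol set, which section 14.3 opens as "All subjects who have successfully completed all visits".

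**The concern.** Covariate adjustment suits a comparison between lenses. An absolute mean compared with a constant is a different case. The LS mean at the sample mean baseline is essentially the raw Test mean, and that raw mean varies from sample to sample partly because the sample's mean baseline varies. The usual LS-mean standard error treats the mean baseline as a known constant and counts only the variance left after regression on baseline.

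The interval would then be narrower than a 95% interval for the mean in section 2.3, and the one-sided error of a primary test could exceed the 2.5% implied by its rule. The same interval would probably be quoted as the precision of the Test lens's CLUE vision score.

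**Working it through.** **Inputs.** SD 19.58 and planning mean 60.1 (section 14.2, historical Control data, with Test assumed similar); n = 70 completers (section 4.3); threshold 40 (section 14.5). The documents do not give ρ, the correlation of baseline with Test CLUE, nor the number of sites or the site variance. All three are assumed and shown as ranges. The plan gives no power or interval width for hypothesis 1 (Table 5 covers only non-inferiority), so there is no plan figure to reproduce.

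**Step 1: variance, leaving site aside.**
- Sampling variance of the Test mean: SD²/n.
- Variance used by the adjusted interval: SD²(1 − ρ²)/n.
- Part left out: slope² × var(baseline)/n = ρ²SD²/n.
- So the SE is too small by the factor √(1 − ρ²).

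Full SE = 19.58/√70 = 2.340, and 95% half-width = 1.96 × 2.340 = 4.59.

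Coverage of the adjusted interval = 2Φ(1.96√(1 − ρ²)) − 1. One-sided error = 1 − Φ(1.96√(1 − ρ²)).

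**Step 2: with the random site effect that section 14.5 requires.** Simulation with n = 70, 5 to 10 sites, and site variance 0 to 5% of the total.

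| ρ (assumed) | No site: half-width | No site: coverage | No site: one-sided error | With site: coverage | With site: one-sided error |
|---|---|---|---|---|---|
| 0.3 | 4.38 | 93.8% | 3.1% | about 95–97% | about nominal |
| 0.5 | 3.97 | 91.0% | 4.5% | about 93–95% | see below |
| 0.6 | 3.67 | 88.3% | 5.8% | about 92–93% | about 3–4% |
| 0.8 | 2.75 | 76.0% | 12.0% | about 83–91% | about 6–10% |

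The unadjusted interval with site held about 95–98%. Site helps because an estimated site variance widens the interval for an absolute mean and lowers its degrees of freedom.

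A second run, with 5 or 8 sites and a different approximation to the degrees of freedom, gave 94–96% at ρ = 0.3, 92–94% at 0.5 (one-sided error 3.1–3.9%) and 86–87% at 0.7. Neither run uses exact Kenward-Roger degrees of freedom, so the with-site figures are good to a point or two.

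**Step 3: the hypothesis 1 decision.** (60.1 − 40)/2.340 = 8.6 standard errors above the threshold, so the test passes either way at the planning mean. Without site, the smallest passing observed mean is 40 + 3.67 = 43.67 adjusted against 40 + 4.59 = 44.59 unadjusted at ρ = 0.6, and 42.75 against 44.59 at ρ = 0.8. Only an observed mean a few points above 40 could give different answers.

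**Step 4: hypothesis 2.** One baseline value per subject is the same in both periods and cancels from Test minus Control when both scores are present. In three simulated trials, under compound symmetry and unstructured covariance with random site, the lens difference and its SE agreed to four decimals with and without baseline (for example 1.3172, SE 2.0716).

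**The case against.** **The evaluation point is inferred.** The plan never says where the adjusted mean is evaluated, and an interval conditional on the observed baselines is valid on its own terms. That stands. But the conditional mean is not the quantity named in section 2.3, and leaving the choice open in a primary decision rule is itself a gap.

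**ρ may be small.** Baseline is rated on habitual correction, which may be monovision, multifocals, readers over contact lenses, or no presbyopic correction at all. Table 5's intra-class correlations concern two study lenses in one crossover and cannot be read across. That stands. At ρ = 0.2 the half-width is 4.49 against 4.59, which is trivial.

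**The larger figures.** A reader might infer coverage of 88% at ρ = 0.6 and 76% at ρ = 0.8. Those apply to a model without site. Section 14.5 includes site, and with it the shortfall is smaller and disappears at about ρ = 0.3.

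**False study success.** A reader might also infer that the trial could wrongly succeed. Section 2.3 requires every primary and secondary hypothesis to be met. With Test truly at 40 and Control at 60.1, the difference is −20.1. At the lowest Table 5 correlation (0.3) its SE is 19.58 × √(2 × 0.7/70) = 2.77. Passing non-inferiority then needs a normal deviate above (20.1 − 5)/2.77 + 1.96 = 7.4, a probability below 10⁻¹². Even with Control at 50 it is below 0.0001. This objection stands.

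**Hypothesis 2.** That baseline adds no precision there with complete pairs might be read as a defect. It is not one: the covariate does no harm. It can also contribute when a score is missing, because the per-protocol set requires completed visits rather than completed questionnaires.

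**Conclusion.** The mismatch is real but modest. Hypothesis 1 is stated for the mean Test score, and its planned interval, on the usual LS-means reading, leaves out one source of that mean's sampling variance. With site in the model the effect is negligible at ρ of about 0.3, a point or two of coverage at 0.5, two to three points at 0.6, and 4 to 12 points at 0.8.

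These sizes rest on assumed values for ρ, the number of sites and the site variance, and on evaluation at the sample mean baseline. Confidence is therefore moderate as to size. The pass or fail result on hypothesis 1 is not in doubt at the planning mean. What needs correcting is the interval's stated precision and error rate.

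**What to change.** In section 14.5, specify that hypothesis 1 is tested on the Test-lens mean from the same mixed model (lens, period, sequence, random site), without baseline CLUE and without the optional race, gender and ADD covariates, which raise the same problem. Alternatively, keep the adjusted mean, state that it is evaluated at the sample covariate means, and add the variance of those means to its SE; for baseline this is slope² × var(baseline)/n. Leave the hypothesis 2 model unchanged. The first option also matches the core model in section 14.6, which tests Test-lens means against constants and names no baseline covariate.

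The cost is one extra model run and a wider hypothesis 1 interval. In the runs with 5 or 8 sites the half-width grew by about 0.2 points at ρ = 0.3 (for example 5.07 to 5.30), 0.6 to 0.7 at 0.5 (4.58 to 5.30) and 1.3 to 1.5 at 0.7 (3.78 to 5.26). At the planning mean of 60.1 this costs essentially no power.
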